## 6.10. Rescue Therapy

Rescue therapy with additional topical and systemic therapies is available starting after 2 weeks of treatment (Visit 4), for patients who are experiencing worsening and unacceptable symptoms of AD despite treatment with IP and moderate-potency TCS. Patients whose lesions persist or worsen despite the use of emollients and background TCS therapy (e.g., triamcinolone 0.1% cream and/or hydrocortisone 2.5% ointment) and/or patients who require prolonged applications

of triamcinolone 0.1% cream (moderate-potency TCS) on large surfaces may be considered for rescue to high- or ultra-high-potency TCS. If topical rescue therapy as described above fails to sufficiently control AD symptoms, then oral systemic medications may be used as rescue (e.g., corticosteroids, cyclosporine, methotrexate); however, investigational product will be required to be permanently discontinued for the remainder of the 16-week study duration. If these medications are needed for other medical conditions (e.g., asthma flare), they will still be treated as rescue medications.

The initial rescue therapy will be the first non-missing record before the last dose date from the CRF page *Concomitant Therapy: Rescue Therapy*.

A summary of the initial rescue therapy and the reason for requiring initial rescue will be produced, as well as a summary of the proportion of patients initially rescued at each study visit. A summary of all rescue medications will be provided.

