If topical rescue therapy as described above fails to sufficiently control AD symptoms, then oral systemic medications may be used as rescue (e.g., corticosteroids, cyclosporine, and methotrexate); however, investigational product will be required to be permanently discontinued for the remainder of the 16-week study duration. If these medications are needed for other medical conditions (e.g., asthma flare), they will still be treated as rescue medications. These patients are still eligible to enter the long-term extension study (JAHN), if they complete the schedule of study visits through Visit 8 (Week 16) and are also able to complete a minimum 4-week washout from oral systemic rescue medications (which can occur during the screening period for Study JAHN).

Investigators should make every attempt to conduct efficacy and safety assessments immediately before administering any rescue treatment. An unscheduled visit can be used for this purpose if necessary.

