### 6.7. Patient Disposition

An overview of patient populations will be summarized by treatment group. Frequency counts and percentages of patients excluded prior to randomization by primary reason for exclusion will be provided for patients who failed to meet study entry requirements during screening.

Patient disposition through Week 16 will be summarized using the ITT population. Frequency counts and percentages of patients who complete the study treatment visits or discontinue early from the study along with whether they completed follow-up, did not complete follow-up or

enrolled into the extension will be summarized separately by treatment group for patients who are not rescued and for patients who are rescued, along with their reason for study discontinuation. Frequency counts and percentages of patients who complete the treatment or discontinue treatment early will also be summarized separately by treatment group for patients who are not rescued and for patients who are rescued, along with their reason for treatment discontinuation.

A listing of patient disposition will be provided for all randomized patients, with the extent of their participation in the study and the reason for discontinuation. A listing of all randomized patients with their treatment assignment will also be provided.

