## 6.15. Safety Analyses

The general methods used to summarize safety data, including the definition of baseline and postbaseline are described in Section 6.2.

Safety analyses will include data from first dose of the study treatment to after rescue, unless otherwise stated, and patients will be analyzed according to the investigational product to which they were randomized at Visit 2. A sensitivity approach to the safety analyses will use data censored at last dose of the study drug for patients rescued to systemic therapy. These analyses will be conducted for treatment-emergent adverse events (TEAEs), serious adverse events (SAEs), AEs leading to permanent study drug discontinuation and special topics excluding deaths and malignancies. Additional analyses may be conducted using data after rescue to systemic therapy for some safety topics such as systemic TEAEs, and SAEs. Safety analyses will use the safety population defined in Section 6.2.1.

Safety topics that will be addressed include the following: AEs including TEAEs and SAEs, clinical laboratory evaluations, vital signs and physical characteristics, Columbia Suicide Severity Rating Scale (C-SSRS), the Self-Harm Supplement Form, safety in special groups and circumstances, including adverse events of special interest (AESI) (see Section 6.15.5), and investigational product interruptions.

Unless otherwise specified, by-visit summaries will include planned on-treatment visits. For tables that summarize events (such as AEs, categorical lab abnormalities, shift to maximum value), post-last dose follow-up data will be included. Follow-up data is defined as all data occurring up to 30 days (planned maximum follow-up time) after last dose of treatment including rescue, regardless of study period.

For selected safety assessments other than events, descriptive statistics may be presented for the last measure observed during post-treatment follow-up (up to 30 days after the last dose of treatment including rescue, regardless of study period).

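### SAP 6.10 accepts initial rescue only before the last dose date, so its initial-rescue summaries omit any first rescue dated on or after it

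*SAP*

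**What the plan says.** SAP Section 6.10 identifies initial rescue by a date rule on the Rescue Therapy CRF page: "The initial rescue therapy will be the first non-missing record before the last dose date". It then plans summaries of the initial therapy and the reason for it, "as well as a summary of the proportion of patients initially rescued at each study visit". A further output carries no date condition: "A summary of all rescue medications will be provided".

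Protocol Section 7.7.4 sets the sequence for atopic dermatitis (AD): "If topical rescue therapy as described above fails to sufficiently control AD symptoms, then oral systemic medications may be used as rescue". When that happens, "investigational product will be required to be permanently discontinued for the remainder of the 16-week study duration". Systemic drugs given for other reasons are included: "If these medications are needed for other medical conditions (e.g., asthma flare), they will still be treated as rescue medications". SAP Section 6.10 repeats these provisions. Topically rescued patients stay on investigational product (Protocol 7.7.4).

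Protocol Sections 5.1.2 and 8.1.2 keep patients who stop drug in the study to Week 16, so later rescue can be recorded.

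Two other parts of the SAP use rescue status without citing Section 6.10. Section 6.7 gives disposition separately "for patients who are not rescued and for patients who are rescued". Section 6.15 plans a safety sensitivity analysis using "data censored at last dose of the study drug for patients rescued to systemic therapy".

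**The concern.** The rule stops looking for rescue at the point where some rescues begin. Systemic rescue requires drug to stop permanently, so its start can fall on or after the last dose. A patient who has already stopped drug but remains in follow-up can only be rescued after the last dose. The SAP treats these events as rescue, yet its date condition removes them from the initial-rescue summaries.

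At stake is a reported descriptive result: how many patients in each arm needed rescue, when, and why. The omitted patients are not a random subset. They are the ones who stopped drug first or who received a systemic agent, and their number may differ between placebo and active arms.

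**Working it through.** The plan states no rescue rate, so there is no figure to reproduce. The check sets the rule against the possible rescue paths and then gives a range under assumed counts.

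**Paths under the rule**

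1. Topical rescue for AD while on drug, followed by systemic rescue. The topical record is dated before the last dose, so the patient has an initial rescue. Not affected.
2. A systemic drug for another condition, with no earlier topical rescue. If its start is before the last dose date, it counts. If its start is on or after that date, the patient has no initial rescue.
3. Drug stopped for any reason, patient kept in follow-up, first rescue (topical or systemic) given later. The patient has no initial rescue.
4. First rescue dated on the last dose date itself. The wording requires an earlier date, so the patient has no initial rescue.

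Paths 2 (in part), 3 and 4 are dropped from the type, reason and by-visit summaries. All would still appear in the summary of all rescue medications.

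**Size under assumptions**

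Let *a* be the number of patients per arm whose first rescue is before the last dose date, and *b* the number whose first rescue is on or after it. With 100 patients per arm (SAP Section 5.1):

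- proportion shown as initially rescued = *a*/100
- proportion without the cut-off = (*a* + *b*)/100
- share of rescued patients missed = *b*/(*a* + *b*)

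The values of *a* and *b* are assumptions.

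| *a* | *b* | Shown | Without cut-off | Share missed |
|---|---|---|---|---|
| 5 | 0 | 5% | 5% | 0% |
| 5 | 2 | 5% | 7% | 2/7 = 29% |
| 5 | 5 | 5% | 10% | 5/10 = 50% |
| 5 | 10 | 5% | 15% | 10/15 = 67% |
| 10 | 0 | 10% | 10% | 0% |
| 10 | 2 | 10% | 12% | 2/12 = 17% |
| 10 | 5 | 10% | 15% | 5/15 = 33% |
| 10 | 10 | 10% | 20% | 10/20 = 50% |
| 20 | 0 | 20% | 20% | 0% |
| 20 | 2 | 20% | 22% | 2/22 = 9% |
| 20 | 5 | 20% | 25% | 5/25 = 20% |
| 20 | 10 | 20% | 30% | 10/30 = 33% |

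In percentage points the understatement is *b*, here 0 to 10 per 100 patients.

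**Efficacy**

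SAP Section 6.4 censors at permanent discontinuation under both rules. The primary rule adds rescue as a second trigger; the secondary rule does not use rescue. For a patient who has permanently stopped drug, a rescue at or after that point changes neither the censoring nor the nonresponder imputation.

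**The case against.** The best defence is that the definition is deliberate. Protocol Section 7.7.4 and SAP Section 6.10 describe rescue for patients whose disease is not controlled while they take investigational product and background topical corticosteroid. A patient who has already stopped drug is not failing on drug, so an on-drug definition of initial rescue is coherent. This stands as an argument for showing the on-drug count. It does not explain why the SAP counts systemic drugs for other conditions as rescue and then drops some of them by date, and the SAP does not label its summaries as on-drug only.

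The affected group may also be small. For AD, systemic rescue follows failed topical rescue given on drug, so most systemic cases should already have a qualifying record. Nor does either document say that drug must stop before the systemic agent starts. A patient who begins it between visits and keeps taking tablets for some days has a record before the last dose. Protocol Section 7.7.3 also foresees inadvertent use of such drugs, with investigational product continuing by agreement with the sponsor. All of this stands, and it is why the number missed could be zero.

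Finally, rescue after last dose is not lost from reporting, because the summary of all rescue medications has no cut-off. That is correct. But as planned, that summary supplies neither the by-visit proportion nor the reason for initial rescue.

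**Conclusion.** The point holds as a minor one about descriptive reporting. Read literally, SAP Section 6.10 omits every first rescue dated on or after the last dose from three summaries of initial rescue. The understatement equals the number of such patients, which cannot be estimated from the documents. The table of shares missed rests wholly on assumed counts and starts at zero.

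A reader might infer more, without support in the documents:

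- **That such rescue is never counted.** The all-rescue-medication summary includes it.
- **That all systemic-first rescues are missed.** Only those starting on or after the last dose are.
- **That the disposition tables misclassify these patients as not rescued.** This is only possible. Section 6.7 neither defines rescued nor refers to Section 6.10, though a programmer could reuse its date rule.
- **That the safety sensitivity analysis is compromised.** The first record is normally topical, so an initial-rescue variable could not identify patients rescued to systemic therapy even without the cut-off. That analysis needs the full rescue records.
- **That the efficacy results change.** Both censoring rules already act at permanent discontinuation.

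**What to change.** In SAP Section 6.10, define initial rescue as the first record on the Rescue Therapy page that starts on or after first dose and on or before the Week 16 or early termination visit, regardless of last dose date. Tabulate records before last dose and records on or after last dose separately. The on-drug count then stays visible, which meets the argument for an on-drug definition. In Section 6.7, state that the rescued and not-rescued groups use this definition.

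The cost is one revised sentence, one cross-reference, a changed date condition in the program and one extra split in the tables. No new data are needed, since the present rule already uses the rescue records and the last dose date. No clinical rule and no inferential analysis changes.

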## 6.11. Previous and Concomitant Therapy

Summaries of previous and concomitant medications will be based on the ITT population.

At screening, previous and current AD treatments are recorded for each patient. Concomitant therapy for the treatment period is defined as therapy that starts before or during the treatment period and ends during the treatment period or is ongoing (has no end date or ends after the treatment period). Should there be insufficient data to make this comparison (for example, the concomitant therapy stop year is the same as the treatment start year, but the concomitant therapy stop month and day are missing), the medication will be considered as concomitant for the treatment period.

Summaries of previous medications will be as follows:

- Previous AD therapies

Summaries of concomitant medications, with sponsor and non-sponsor provided background TCS included, will be as follows:

- General Concomitant medications excluding rescue medicine

### 6.11.1. Background TCS

Background TCS therapy with moderate-potency and/or low-potency TCS (e.g., triamcinolone 0.1% cream and/or hydrocortisone 2.5% ointment) are to be used on active lesions, as described in Section 7.7.3 in the protocol.

The dispensed weight of sponsor-provided TCS tubes for the two different potencies (low and moderate) varies between countries due to different supply regions. Average weights of full tubes were used to determine the dispensed weights for each region. Returned tubes were weighed with cap (without the carton) to determine the amount of TCS in grams (g) used at each visit.

For low potency TCS, the dispensed tube weight with cap (without the carton) in Japan is 13.5g. For countries supplied by European distributors (Austria, Germany, Italy, Poland, and Spain), the dispensed weight of low potency TCS is 21g. The remaining countries, supplied by US distributors (Argentina, Australia, Korea, and Taiwan), the weight of low potency TCS is 40g.

For moderate potency TCS, the dispensed tube weight with cap (without the carton) in Japan is 13.5g. For countries supplied by European distributors, the dispensed weight of moderate potency TCS is 38g. The remaining countries, supplied by US distributors, the weight of moderate potency TCS is 40g. The total amount of background TCS, provided by sponsor, will be summarized in grams by potency (low and moderate) and both potencies, between visits (Week 0 through Week 1, Week 1 through Week 2, Week 2 through Week 4, Week 4 through Week 8, Week 8 through Week 12, Week 12 through Week 16), and throughout the entire 16-week treatment period. If a returned tube is not weighed or not returned, then the tube can be classified as partially used, fully used, unused, or unknown. Partially used rescue medication tubes will be defined as 50% used whereas fully used and unused tubes will be defined as 100% and 0% used respectively. When drug accountability is not performed for a particular tube of rescue medication or an answer of 'unknown' is given for a tube which is not returned, that particular tube will not be included in the analysis. The main analysis on the total amount of background TCS throughout the entire 16-week treatment period will apply censoring rule #1. After patients who get rescued or discontinue IP, whichever is earlier, it is assumed that they would use the same amount of TCS as they did before. Analysis will be done via analysis of variance (ANOVA), with geographic region, baseline disease severity and treatment as factors in the model. The secondary analysis will apply censoring rule #2 with the same assumptions as described above.

Whether any background TCS is used or not used for each patient is also collected on the diary device in each day starting from the first dose date throughout the study.

The total number of days that the patients did not use background TCS will be summarized by both potencies throughout the entire 16-week treatment period. The main analysis applies censoring rule #1. After patients who are rescued or discontinue IP, it is assumed that background TCS would be applied each day. In case of missing values in the daily diary, it will be assumed that background TCS has been used. Analysis will be done via ANOVA, with geographic region, baseline disease severity and treatment as factors in the model. A secondary analysis will apply censoring rule #2, with the same assumptions for missing values as described above.

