- Where providing triamcinolone 0.1% cream and/or hydrocortisone 2.5% ointment is not possible, an equivalent-potency TCS cream and/or ointment that is in line with local practices can be supplied by the sites. Refer to [Appendix 8](#) for guidance on potency equivalence.

- Where possible, TCS use when supplied by the site should also be recorded via weight of returned tubes, as indicated in the Schedule of Activities (Section 2); however, where this is not practical, this information does not need to be recorded, and will not be considered a protocol violation.
- If the TCS supplied by the sponsor is not considered suitable for an individual patient, an equivalent-potency TCS cream and/or ointment that is in line with local practices can be supplied by the sites. Refer to [Appendix 8](#) for guidance on potency equivalence.

Choice of High- and Ultra-High-Potency Topical Corticosteroids for Rescue

The use and choice of specific high- or ultra-high-potency TCS for rescue is at the discretion of the investigator and it will not be provided by the sponsor. The weights of returned tubes of the high- and ultra-high-potency TCS are not required.

Other Topical Treatments

Investigators may also select to use TCNIs and/or crisaborole in countries where approved, in place of TCS. If TCNIs or crisaborole are prescribed, use should be limited to problem areas (e.g., face, neck, skin folds, genital areas, etc.).

Use of all topical treatments for AD must be recorded in the CRF.

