#### 4.2.2. Other Secondary Objectives

These are prespecified objectives that will not be adjusted for multiplicity.

Objectives	Endpoints
To test the hypothesis that baricitinib 2 mg QD + TCS or baricitinib 4 mg QD + TCS is superior to placebo + TCS in the treatment of patients with moderate to severe AD.	
 
• Proportion of patients achieving IGA of 0 or 1 with a <math>\geq 2</math>-point improvement at Week 4
 

To compare the efficacy of baricitinib 2 mg QD + TCS or baricitinib 4 mg QD + TCS to placebo + TCS in AD during the 16-week double-blind placebo-controlled period as measured by signs and symptoms of AD.	
 
• Proportion of patients achieving EASI50 at 16 weeks
 
• Proportion of patients achieving IGA of 0 at 16 weeks
 
• Mean change from baseline in SCORAD at 16 weeks
 
• Proportion of patients achieving SCORAD90 at 16 weeks
 
• Mean change from baseline in BSA affected at 16 weeks
 
• Proportion of patients developing skin infections requiring antibiotic treatment by Week 16
 
• Mean gram quantity of background TCS used over 16 weeks (tube weights)
 

To compare the efficacy of baricitinib 2 mg QD + TCS or baricitinib 4 mg QD + TCS to placebo + TCS in AD during the 16-week, double-blind, placebo-controlled treatment period as assessed by patient-reported outcome/QoL measures.	
 
• Percent change from baseline in Itch NRS at 2 days, 1 week, 4 weeks, and 16 weeks
 
• Mean change from baseline in Itch NRS at 2 days, 1 week, 4 weeks and 16 weeks
 
• Proportion of patients achieving a 4-point improvement from baseline in Skin Pain NRS at 16 weeks
 
• Mean change from baseline in the total score of the POEM at 16 weeks
 
• Mean change in the PGI-S-AD scores at 16 weeks
 
• Mean change from baseline in HADS at 16 weeks
 
• Mean change in the DLQI scores at 16 weeks
 
• Mean change in the WPAI scores at 16 weeks
 
• Mean change in the EQ-5D-5L scores at 16 weeks
 
• Mean number of days without use of background TCS over 16 weeks
 

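### Background TCS tubes of unknown use are left out of the gram total, which scores them as 0 g and understates grams in any arm where such a tube was used

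*SAP*

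**What the plan says.** Mean grams of background TCS over 16 weeks, from tube weights, is an other secondary endpoint (Protocol Section 4; SAP 4.2.2), not adjusted for multiplicity. SAP 6.11.1 makes it a total: "The total amount of background TCS, provided by sponsor, will be summarized in grams by potency (low and moderate) and both potencies", by interval between visits and over the whole 16 weeks. Returned tubes are weighed against a fixed dispensed weight. If a tube is not weighed or not returned, "then the tube can be classified as partially used, fully used, unused, or unknown". Partially used tubes "will be defined as 50% used whereas fully used and unused tubes will be defined as 100% and 0% used respectively".

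The last category has its own rule. It opens "When drug accountability is not performed for a particular tube of rescue medication", adds the case of an unreturned tube answered as unknown, and ends "that particular tube will not be included in the analysis".

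After rescue or discontinuation of investigational product, the main analysis assumes that use continues as before. The secondary gram analysis changes only the censoring rule. For the companion endpoint, days without TCS, the same section says: "In case of missing values in the daily diary, it will be assumed that background TCS has been used".

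**The concern.** The exclusion works on the tube, not on the patient or the interval. The patient's total is still computed and enters the ANOVA as if complete. A tube about which nothing is known is therefore treated as one known to be unused.

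The general missing-data methods of SAP 6.4 do not repair this. The total is never flagged as missing, so they have nothing to act on. Tables JAIY.6.5 and JAIY.6.7 list no sensitivity analysis for grams. The region, severity and treatment factors of the ANOVA do not correct a loss that differs by arm. The assumption of unchanged use after rescue or discontinuation carries an earlier undercount forward.

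At stake is the reading of a TCS-sparing result: mean grams in each arm, and the difference between arms.

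**Working it through.** **Plan's own figure.** The documents give none for unknown tubes or expected grams. Their one sample-size figure, 89% power for the primary endpoint, reproduces (0.891 by exact enumeration of the Fisher test, 10% vs 30%, 100 per arm, two-sided 0.025). It does not bear on this point.

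**Step 1: what one tube contributes.** Patient total = Σ (fraction used × grams in tube). A tube left out adds 0 g, and so does an unused tube at 0%. The SAP's dispensed weights (with cap) give the scale:

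| Supply | Dispensed weight | Under the rule | At 50% | At 100% |
|---|---|---|---|---|
| Japan, both potencies | 13.5 g | 0 g | 6.75 g | 13.5 g |
| Europe, low | 21 g | 0 g | 10.5 g | 21 g |
| Europe, moderate | 38 g | 0 g | 19 g | 38 g |
| Other countries, both potencies | 40 g | 0 g | 20 g | 40 g |

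The last two columns are ceilings, because these weights include tube and cap.

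**Step 2: what an arm mean becomes.** Let u be the share of an arm's used grams that sits in unknown tubes. The expected arm mean is true mean × (1 − u). This u equals the share of tubes only if unknown tubes held the same average use as the others in that arm.

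**Step 3: what the difference becomes.** With true means P (placebo) and B (baricitinib):

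observed difference = P(1 − u_P) − B(1 − u_B) = (P − B) − (P·u_P − B·u_B)

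Equal shares give (P − B)(1 − u), a pull towards no difference. With unequal shares, the difference is understated when placebo loses more grams and overstated when baricitinib does.

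**Step 4: illustration.** All means and shares here are assumptions. Take P = 150 g, B = 120 g, true difference 30 g.

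- Equal u of 5%, 10%, 20%: 30 × 0.95 = 28.5 g; 30 × 0.90 = 27 g; 30 × 0.80 = 24 g.
- u_P = 15%, u_B = 5%: 150 × 0.85 − 120 × 0.95 = 127.5 − 114 = 13.5 g.
- u_P = 5%, u_B = 15%: 150 × 0.95 − 120 × 0.85 = 142.5 − 102 = 40.5 g.
- No true difference, 150 g in both arms, shares 5% and 15%: 142.5 − 127.5 = 15 g of apparent difference, in either direction depending on which arm loses more.

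**The case against.** The strongest reply is that the rule is residual. Returned tubes are weighed, and a tube not weighed or not returned is first placed in the 50%, 100% or 0% class where possible. Nothing in the documents suggests that many tubes fall through. The trial is double-blind, and no passage suggests that accountability differs by arm. With equal shares the bias is towards no difference, which is conservative for a superiority claim. All this stands and limits the expected size, but it does not make 0 g a sound value for a tube of unknown use.

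Some stronger readings are tempting but not supported:

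- **Grams are understated in every arm.** That needs used unknown tubes in every arm. A second error could also run the other way: if the 50% and 100% values are applied to weights that include tube and cap, packaging counts as cream. The SAP does not state the base.
- **The comparison is distorted in favour of baricitinib.** Anything beyond shrinkage needs unequal loss by arm, which the documents do not show.
- **The two TCS endpoints contradict each other.** Counting a missing diary day as use goes the opposite way from dropping a tube, but a diary day and a tube are different kinds of missing data and nothing obliges one rule. The days endpoint is in fact a check that does not rest on tube weights.
- **Weighed site-supplied tubes should be added to the total.** Protocol 7.7.2 lets sites supply TCS and, where weighing is not practical, says "this information does not need to be recorded". The SAP openly limits the total to sponsor-provided TCS and puts other background TCS in the concomitant-medication summaries (6.11). Only returned tubes are weighed, and the SAP gives full-tube weights for sponsor tubes alone, so site tubes have no starting weight. Setting those intervals to missing would leave 16-week totals undefined for the ANOVA.

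The rule's reference to rescue medication could suggest that it does not govern background tubes. But it sits in the background TCS section, and Protocol 7.7.2 says that rescue TCS is not sponsor-provided and that its returned weights are not required. Background TCS is the only workable reading.

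**Conclusion.** The point holds as a stated rule that gives a wrong total. Each tube of unknown use is scored as 0 g, and grams are understated in any arm where such a tube was used. The difference shrinks by (1 − u) if the share of used grams in unknown tubes is equal, and can move either way if it is not. The real size cannot be known from the documents: 13.5 g and 40.5 g against a true 30 g show sensitivity under assumed values and are not estimates. No direction of bias between arms is claimed. The primary and key secondary analyses and the 89% power are untouched. The point is worth correcting because the SAP already assigns values to partly used tubes and lacks one only for unknown tubes.

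**What to change.** In SAP 6.11.1:

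1. Replace the exclusion with imputation. Give an unknown tube the patient's own mean grams used per tube of that potency, or the blinded region-by-potency mean if the patient has none. This assumes that unaccounted tubes resemble accounted ones, hence item 2.
2. Report sensitivity bounds with unknown tubes at 0% and at 100% used. Apply percentages to net cream weight, not to the weight with tube and cap.
3. Report the number of unknown tubes by arm, so that readers can see whether the loss is even.
4. Correct rescue medication to background TCS in these sentences.
5. State that the total covers sponsor-provided TCS only, and report by arm how many patients used site-supplied TCS.

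The cost is SAP wording, a little more programming and one added sensitivity table. No new data collection from patients is needed, but net cream weights must be obtained for the tubes supplied, since the documents give only weights with cap.

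### Background-TCS tubes left out of a patient's gram total count as 0 g, so this rule understates TCS use

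*SAP*

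**What the plan says.** SAP section 4.2.2 lists among the other secondary endpoints, which are not adjusted for multiplicity: "Mean gram quantity of background TCS used over 16 weeks (tube weights").

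SAP section 6.11.1 defines the quantity as a total: "The total amount of background TCS, provided by sponsor, will be summarized in grams by potency (low and moderate) and both potencies, between visits", and also over the whole treatment period. Arms are compared by ANOVA with region, baseline severity and treatment as factors.

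For tubes without a weight, the same section says: "If a returned tube is not weighed or not returned, then the tube can be classified as partially used, fully used, unused, or unknown". Three of these four classes receive a value: "Partially used rescue medication tubes will be defined as 50% used whereas fully used and unused tubes will be defined as 100% and 0% used". The rest are excluded. There are two triggers: no accountability was done for the tube, or the tube did not come back and its status was answered as unknown. In either case, the SAP states, "that particular tube will not be included in the analysis".

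Two further rules in section 6.11.1 matter here:

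- After rescue or discontinuation of investigational product, the patient is assumed to go on using the same amount of TCS as before.
- For the companion endpoint, days without background TCS, a missing diary day counts as a day on which TCS was used.

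The tube sentences speak of rescue medication. Protocol section 7.7.2 says that high- and ultra-high-potency rescue TCS is not provided by the sponsor, and adds: "The weights of returned tubes of the high- and ultra-high-potency TCS are not required". The tube rule can therefore only work for background TCS.

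**The concern.** The exclusion acts on the tube, not on the patient or the visit interval. Nothing in section 6.11.1 sets the affected total to missing, rescales it for the lost tube, imputes the tube or bounds the result. In a mean per tube, dropping an unknown tube could be neutral. In a sum it is not: the tube adds nothing, exactly like a tube recorded as unused. Absence of information is turned into a finding of no use.

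At stake are the mean grams in each arm and the difference between them. This endpoint helps the reader judge whether efficacy results were obtained with more or less background steroid. The section also treats its two TCS-use endpoints in opposite ways, without explanation: a missing diary day pushes apparent use up, and a missing tube pushes it down.

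**Working it through.** The documents state no expected grams, standard deviation, tubes per patient or rate of unaccounted tubes, so there is no figure in the plan to reproduce. What follows is direct arithmetic. Every input that is not a tube weight or a percentage-used rule from SAP section 6.11.1 is an assumption.

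**1. Form of the total.** Patient total = sum over tubes of (share used × tube weight). A tube left out contributes 0. A tube classed as unused contributes 0% × weight = 0. The two are identical.

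**2. Loss per excluded tube.** Loss = true share used × weight. With the dispensed weights in the SAP:

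| Supply | Weight | 0% used | 50% used | 100% used |
|---|---|---|---|---|
| Japan, both potencies | 13.5 g | 0 | 6.75 g | 13.5 g |
| Europe, low | 21 g | 0 | 10.5 g | 21 g |
| Europe, moderate | 38 g | 0 | 19 g | 38 g |
| Other countries, both potencies | 40 g | 0 | 20 g | 40 g |

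The weights include tube and cap, so these gram losses are upper bounds. The loss is never negative, and is zero only when the tube was truly unused.

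**3. Patient level.** If k of T equal tubes are excluded and were used like the others, the total is low by k/T. Assume 38 g tubes, half used (19 g each):

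- T = 4, k = 1: 3 × 19 = 57 g instead of 4 × 19 = 76 g, 25% low.
- T = 8, k = 1: 7 × 19 = 133 g instead of 8 × 19 = 152 g, 12.5% low.
- T = 4, k = 2: 2 × 19 = 38 g instead of 76 g, 50% low.

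**4. Forward projection.** Suppose the first of these patients is rescued at Week 8 and the earlier rate is carried through the remaining 8 weeks. The recorded total is 2 × 57 = 114 g instead of 2 × 76 = 152 g. The shortfall doubles from 19 g to 38 g.

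**5. Arm level, as a share.** Let u be the share of tubes excluded, m the mean share used of the other tubes and m_u that of the excluded tubes. Then

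understatement = u·m_u / [(1 − u)·m + u·m_u].

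- If m_u = m, this reduces to u: 5%, 10% or 20% for assumed u of 5%, 10% or 20%.
- If the excluded tubes had been emptied (m_u = 1.0, with assumed m = 0.6): 0.05/0.62 = 8.1%, 0.10/0.64 = 15.6%, 0.20/0.68 = 29.4%.

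**6. Difference between arms.** Assume true means of 200 g (placebo) and 150 g (baricitinib), a difference of 50 g:

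| Loss, placebo / baricitinib | Recorded means | Difference |
|---|---|---|
| 10% / 10% | 180 / 135 g | 45 g |
| 15% / 5% | 170 / 142.5 g | 27.5 g |
| 5% / 15% | 190 / 127.5 g | 62.5 g |

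**The case against.** Several points on the other side stand:

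- **Direction between arms.** A reader might infer that the rule always pulls the arms together, because the arm using more TCS handles more tubes. The documents do not support this. It follows if the excluded shares are equal or higher in the heavier-using arm. If the share is higher in the other arm, the difference can grow, as in the third row of the last table.
- **Test and ratio.** With equal proportional loss, the standard deviation scales with the means. The ratio of means is unchanged, and so, to first order, is the ANOVA test statistic. The loss then falls on the grams reported, with some added noise from uneven loss across patients.
- **Patients with no evaluable tube.** A reader might infer that such a patient is totalled as 0 g. The SAP does not say so. A missing total is at least as natural a reading, and the text is silent.
- **Reach of the rule.** Not every tube of unknown status is dropped. The unknown clause covers tubes that were not returned, and the other trigger is accountability not performed. Many unweighed tubes will first be classed as full, partial or unused. A returned, unweighed tube marked unknown has no stated rule unless it counts as accountability not performed.
- **Importance.** The endpoint covers sponsor-provided TCS only, and Protocol section 7.7.2 does not require site-supplied TCS to be recorded where that is impractical. It was never a complete measure. The diary endpoint gives a second view under the opposite missing-data assumption.
- **Wording.** The reference to rescue medication is an editorial slip, and context makes the meaning clear.

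None of this supplies a value for an excluded tube. The alternative censoring rule in the secondary analysis does not do so either, since it keeps the same tube rule.

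**Conclusion.** The point holds for patient totals and arm means: this rule can only lower them, and leaves them unaffected only if no tube is excluded or every excluded tube was unused. The understatement equals the excluded share when those tubes were used like the others, so 5% to 20% over the assumed range, and more if they tended to be emptied. The true size is unknown and could be negligible, because the documents give no rate. Neither a fixed direction for the treatment difference nor an automatic 0 g for a patient without evaluable tubes can be claimed from the text.

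The conclusion concerns one endpoint without multiplicity adjustment and leaves primary and key secondary inference alone. It is still worth correcting, because the endpoint is listed, has a planned between-arm test, and the rule as written is biased in a known direction.

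**What to change.** In SAP section 6.11.1:

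1. Replace the exclusion with imputation. Give a tube without accountability, or with unknown status, the mean grams used per tube over that patient's other tubes of the same potency. If there are none, use the blinded pooled mean for that potency and supply region. State that this covers returned but unweighed tubes marked unknown, so that a patient with no evaluable tube is not totalled as 0 g. Apply it before use is projected forward after rescue or discontinuation.
2. Add two bounding runs, with these tubes at 0% and at 100% used. Base 100% on net contents, because the weights in the SAP include tube and cap.
3. Change rescue medication to background TCS in the two tube sentences.

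The cost is SAP wording and a few lines of programming before unblinding, with no new patient data. Net tube contents are not given in the SAP and would have to be added. Section 6.11.1 was already revised in SAP Version 2, so an edit of this kind is practicable. The downside is that single imputation brings a modest assumption of its own, which the bounding runs address.
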